End Points:

Complete recovery of facial nerve function

Time to complete recovery of facial nerve function

Improvement of facial nerve function within 3 weeks

Time to initial improvement of facial nerve function

Adverse effects related to the treatment

Methodology:

Screening

Patients age 18-99 will be identified in clinic as having an acute facial nerve paralysis of H-B IV or greater. Symptoms must have developed within a 72 hour period and be present for the last 21 days or less.

Baseline assessment

Patients who meet criteria will undergo a complete history, head, neck, and cranial nerve exam. Facial function will be evaluated with H-B scoring system. In patients where there is a suspicion of Lyme disease, Lyme disease serology will be performed. Electroneurography (ENoG) and electromyography (EMG) testing will be performed on patients with complete paralysis only.

Treatment Phase

Participants in groups 1 & 2 will be treated with steroids (prednisone 60 mg for 5 days followed by a 5 day taper). Patients will then be randomized into either control group (Group 1) or treatment group (Group 2). Patients in Group 2 will undergo intratympanic steroid injection. An audiogram and tympanography testing will be performed prior to injections.

Participants unable to take oral steroids for medical reasons (such as diabetes) will be placed in Group 3. These participants will receive intratympanic steroid injections only. An audiogram and tympanography testing will be performed prior to injections.

Injection will be up to 1cc of dexamethasone 24mg/mL. The procedure will be performed at supine position under a microscope. Local anesthesia will be achieved with topical phenol. A myringotomy will be made in the tympanic membrane. A 1 mL syringe connected to a needle will be used to slowly inject between 0.2 cc and 1.0 cc of solution through the myringotomy, with the subject's head turned 45 degrees to the opposite side. The subject will be asked to maintain positioning for at least 30 minutes and refrain from swallowing. The dose administered will vary due to subject-specific factors.

Follow-Up

Patients will be evaluated once a week for the first month after completion of treatment. From that point, patients will be evaluated monthly until complete recovery.

Procedures:

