Participants are identified in clinic to have idiopathic facial nerve paralysis. If they meet inclusion criteria, they will then be asked to participate in the study and sign the consent form. Participants will undergo a complete medical history including facial nerve paralysis history, head, neck, and cranial nerve exam. Facial function will be evaluated with H-B scoring system. Lyme disease serology will be drawn on patients for which there is a suspicion of Lyme disease (SOC). Electroneurography (ENoG) and electromyography (EMG) testing will be performed only on patients with complete paralysis, as part of the standard of care (SOC) work-up. Next, patients in Groups 1 & 2 will be prescribed a course of oral prednisone. They will be randomized to Group 1 or Group 2. If randomized to Group 1, patient will come back weekly for a month for evaluation of facial nerve function. If randomized to Group 2 or placed into Group 3, patients will undergo an audiogram and tympanometry testing, which is SOC prior to any intratympanic injection. Patients will undergo intratympanic steroid injection to affected side after all details and risks of each procedure are discussed. There will be one injection every 3-7 days over the course of 3 weeks for a total of 3 injections. Follow-up will be once a week for the first month after the completion of treatment. From that point, patients will be evaluated monthly. All patients Group 2 & 3 will undergo a post-procedure audiogram and tympanogram approximately 1 month following the 3rd injection, which is SOC. Follow-up will be completed once full facial nerve recovery to H-B I or for up to one year, whichever comes first. At each clinic visit patients will undergo a complete head and neck exam, including H-B score. Extensive review of systems will be completed at every visit. Facial nerve exams will be video recorded pre-treatment and all post-treatment follow-up visits to allow for 2 independent blinded reviewers to determine facial nerve recovery and H-B score; a third unblinded review will be performed by the treating physician.

Adverse effects of the treatment will be assessed at each visit.

7. Selection and Withdrawal of Subjects

Inclusion Criteria:

1. 18 to 99 years
2. English as primary language
3. Acute unilateral facial palsy without skin lesions which developed within a 72-hour period and is present for 21 days or less.
4. Moderate to severe facial palsy [House-Brackmann grade IV or greater]

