Protocol: *Facial Nerve Study*

PI: [name]

Exclusion Criteria:

1. Another cause of facial nerve paralysis that is not idiopathic
2. Otologic disease including otitis media, temporal bone fracture, a previous history of facial nerve palsy in either side, history of otologic surgery, and suspected Ramsay Hunt syndrome.
3. Systemic disease including history of tuberculosis, history of head and neck cancer, other neurological disorders, recent use of ototoxic medications, liver or renal dysfunction, and other illnesses that would contraindicate the use of high-dose steroid therapy.
4. Pregnancy

Withdrawal Criteria:

Subjects may withdraw from the study at any time without prejudice to their care. They may also be discontinued from the study at the discretion of the Investigator for lack of adherence to study treatment or visit schedules or adverse events. The Investigator may also withdraw subjects who violate the study plan, or to protect the subject for reasons of safety or for administrative reasons. It will be documented whether or not each subject completes the clinical study. If the Investigator becomes aware of any serious, related adverse events after the subject completes or withdraws from the study, they will be recorded in the source documents and on the case report form.

8. Treatment of Subjects

Participants in Groups 1 & 2 will be treated with steroids (prednisone 60 mg for 5 days followed by 5 day taper) as defined by the current standard of care. Patients in Group 1 will not have any further treatment. Patients in Group 2 & 3 will undergo intratympanic steroid injection. The patient will undergo one injection every 3-7 days over the course of 3 weeks for a total of 3 injections.

9. Costs

Participants will not be paid to be a part of the study. Subjects will be responsible for the normal cost of treatment associated with facial nerve paralysis, including any tests that the physician feels are necessary and all medications. Subjects who are randomized to one of the groups to receive the intratympanic injections will not be responsible for the added costs of the injection (which include the medication and phenol), the audiogram and tympanometry, and extra office visits to receive each injection.

10. Assessment of Efficacy

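### The randomised arms have different House-Brackmann assessment days, so the two improvement end points can differ between arms with no true effect, in either direction

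*Combined protocol and SAP*

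**What the plan says.** Section 6 (End Points) lists "Improvement of facial nerve function within 3 weeks" and "Time to initial improvement of facial nerve function". It does not define improvement, name the reading that dates it, or give a day zero.

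The assessment schedule has to be pieced together:

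- **When the scale is scored.** Section 6, Procedures: "At each clinic visit patients will undergo a complete head and neck exam, including H-B score".
- **Group 1.** Section 6, Procedures: "If randomized to Group 1, patient will come back weekly for a month for evaluation of facial nerve function". The sentence follows randomisation, but no start day is given.
- **Group 2.** Section 6, Procedures: "There will be one injection every 3-7 days over the course of 3 weeks for a total of 3 injections". Section 8 repeats the 3-7 day interval; section 2 gives 3-4 days. Section 9 (Costs) confirms that these are additional attendances: "extra office visits to receive each injection".
- **Follow-up clock.** Section 6, Follow-Up: "Patients will be evaluated once a week for the first month after completion of treatment". Treatment ends on different days in the two arms: after a 10-day prednisone course in Group 1, and after the third injection in Group 2 when that comes later.
- **Blinded reading.** Section 6, Procedures: "Facial nerve exams will be video recorded pre-treatment and all post-treatment follow-up visits". Injection visits are not listed. The treating physician adds an unblinded review. Section 10 (Assessment of Efficacy) has two blinded assessors determine efficacy from video.

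**The concern.** Both early end points record the first visit at which improvement is seen, so they depend on when and how often a patient is looked at as well as on recovery itself. If the looks fall on different days in the two arms, the recorded times and the proportions by day 21 can differ with identical true recovery. Time to complete recovery shares the problem, to a lesser degree.

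This bears on the trial's second question in section 5, whether the injection hastens recovery. Section 13 counts these end points among the objective measures that make the unblinded trial reliable. Randomisation does not protect against a measurement schedule that itself differs by arm.

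**Working it through.** The documents give no figure for this point. The sample size in section 11 concerns complete recovery and does not enter.

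**Step 1: visit days up to day 21.** Assumption: day 0 is baseline and, in Group 2, the first injection. Weekly follow-up in Group 2 starts after the third injection.

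| Reading of the schedule | Post-baseline readings by day 21 |
|---|---|
| Group 1, weekly from randomisation | 7, 14, 21 |
| Group 1, weekly after 10 days of prednisone | 17 |
| Group 2, 3-day spacing | 3, 6 (injection); 13, 20 (video) |
| Group 2, 4-day spacing | 4, 8 (injection); 15 (video) |
| Group 2, 7-day spacing | 7, 14 (injection); 21 (video) |

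If the injections instead fell on days 7, 14 and 21, Group 2 would have no video reading after baseline by day 21.

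**Step 2: proportion recorded as improved by day 21 with no true effect.** Assumptions, none from the documents: true time to improvement is exponential with median 21 days in both arms; improvement persists; each reading before true improvement is falsely scored as improved with probability f. With k readings, the last on day L,

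P(improved by day 21) = 1 − 2^(−L/21) × (1 − f)^k.

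No misreading (f = 0; only L matters):

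- Group 1 from randomisation: 1 − 2^(−21/21) = 50.0%
- Group 1 after prednisone: 1 − 2^(−17/21) = 1 − 0.5706 = 42.9%
- Group 2, 3-day: 1 − 2^(−20/21) = 1 − 0.5168 = 48.3%
- Group 2, 4-day: 1 − 2^(−15/21) = 1 − 0.6095 = 39.0%
- Group 2, 7-day: 50.0%

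With f = 0.10:

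| | All visits count | Video visits only |
|---|---|---|
| Group 1 from randomisation | 1 − 0.5 × 0.9³ = 63.6% | same |
| Group 1 after prednisone | 1 − 0.5706 × 0.9 = 48.6% | same |
| Group 2, 3-day | 1 − 0.5168 × 0.9⁴ = 66.1% | 1 − 0.5168 × 0.9² = 58.1% |
| Group 2, 4-day | 1 − 0.6095 × 0.9³ = 55.6% | 1 − 0.6095 × 0.9 = 45.1% |
| Group 2, 7-day | 1 − 0.5 × 0.9³ = 63.6% | 1 − 0.5 × 0.9 = 55.0% |

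Against Group 1 seen from randomisation, Group 2 is ahead only at 3-day spacing with every visit counted. It is level at 7 days with every visit counted, and behind in the other cells. Against Group 1 seen only after prednisone, Group 2 is ahead in every cell except 4-day spacing with video only.

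**Step 3: time to initial improvement.** Section 11 names no test, so a log-rank test is used for illustration, in a no-effect simulation with 30 per arm.

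- Median 21 days, f = 0.10, Group 1 weekly from randomisation, all visits counted: the test favours Group 2 in about 16% of trials at 3-day spacing and 4-6% at 4- to 7-day spacing, against a nominal 2.5% per side.
- Same setting, video visits only: it favours Group 1 in about 7-33% of trials.
- Group 1 first seen on day 17, all visits counted, no misreading, median 14 or 21 days: false positives are 8-40% two-sided against a nominal 5%, favouring Group 2.

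**Step 4: after aligning the schedules.** With the same days (7, 14, 21) and the same readings counted in both arms, the proportions are equal: 50.0% each with f = 0, and 63.6% each with f = 0.10.

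**The case against.** The strongest reply is section 10: two blinded assessors determine efficacy from video. Injection visits have no planned video, so on a plain reading their scores never reach the end points, and the instruction to score at each visit describes the clinical examination. This stands in large part. It does not align the arms, however. With video only, Group 2's first counted reading falls on day 13, 15 or 21, against day 7 for Group 1 if seen from randomisation, and the bias turns against the injection.

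A reader might infer that the injection visits always give Group 2 an advantage. The documents do not support this, for four reasons:

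- Group 2's weekly visits follow the injections and are not added to a day 7, 14, 21 calendar. Five looks by day 21 would give 1 − 0.5 × 0.9⁵ = 70.5% against 63.6%, but the stated sequence gives at most four, and only three at 4- or 7-day spacing.
- A higher proportion improved purely from extra looks requires misreading. With accurate, persistent improvement, only the last visit by day 21 matters.
- The treating physician's unblinded review is not confined to Group 2.
- The number of looks is not the whole problem. The unstated day zero and the arm-specific follow-up clock drive both size and direction.

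It is also fair to say that the primary outcome in section 11, complete recovery followed for up to a year, is scarcely touched.

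**Conclusion.** The concern holds as a difference in assessment schedule between the randomised arms, with a direction that the protocol leaves open.

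- It favours Group 2 if injection-visit scores count and injections are closely spaced, or in most cases if Group 1's visits start only after prednisone.
- It favours Group 1 if only video visits count and Group 1 is seen weekly from randomisation.

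Under the stated assumptions, with Group 1 seen from randomisation and 10% misreading, the no-effect gap by day 21 (Group 2 minus Group 1) runs from +2.5 points (66.1 − 63.6) to −18.5 points (45.1 − 63.6). If Group 1 is first seen on day 17 and all visits count, it reaches +17.5 points (66.1 − 48.6). The misreading rate, the median time to improvement and the actual spacing are assumed, so these figures show scale and are not estimates. That the assessment days differ by arm follows from the text without them. The change should be made before the two improvement end points are used to answer the second trial question.

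**What to change.** Add to section 6: *Improvement and recovery end points are timed from randomisation. House-Brackmann assessments are scheduled on the same days after randomisation in Groups 1 and 2 (for example weekly for the first weeks, then monthly), with video recorded at each. Only the blinded video scores from these visits are used for the end points. Scores from other injection visits, and the treating physician's scores, are kept for care and safety only.*

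Two sets of passages must also be reconciled: the injection interval (3-4 days in section 2; 3-7 days in section 6, Procedures, and section 8), and the weekly follow-up (for a month in Group 1, against a month counted from completion of treatment).

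The cost is more than one sentence, because the protocol has no common calendar and the fix must set one. It means a few extra videos, possibly a visit or two more in Group 2, and some early Group 2 readings left unused. It changes no treatment.

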for Bell's palsy was not published until 2014 (4). It was a randomized control trial that divided patients into standard treatment (oral steroids and acyclovir) versus standard treatment with intratympanic steroid injection. There was not a statistically significant difference between the complete recovery rate of the control group and of the intratympanic steroid group; however, the time to recovery was significantly shorter in the intratympanic steroid injection group as compared to the control group. Limitations of this study include small sample size and high attrition rate.

There have not been any other studies published in the literature looking at improving facial nerve recovery in idiopathic facial nerve paralysis with the use of intratympanic steroid injections.

5. Trial Objectives and Purpose

The question proposed by this study are:

Does intratympanic steroid injection improve the complete recovery rate of patients with idiopathic facial nerve paralysis?

Does intratympanic steroid injection hasten the time to recovery in patients with idiopathic facial nerve paralysis?

Are there significantly more adverse effects with the use of intratympanic steroid injection as compared to oral steroids in patients with idiopathic facial nerve paralysis?

The trial seeks to provide evidence that intratympanic steroid injection are acceptable and successful adjuncts to treatment of idiopathic facial nerve paralysis.

To answer this question, a prospective, single-blinded, randomized trial will be performed. The subjects will be randomized into the treatment group and the control group. The control group will receive oral steroids which is the current standard of care. Patients in the treatment group will receive oral steroids AND intratympanic steroid injections. The patient's will not be blinded because the patient will be undergoing an in-office procedure. It has been found to be unethical to perform sham procedures in patients. A third group of patients will consist of those patients that are unable to take oral steroids for medical reasons. These patients will only receive the intratympanic injection and they are placed in this group for medical reasons only (no randomization into this group). The patients will be examined and scored using House-Brackmann scoring system by a blinded investigator trained in otolaryngology.

6. Trial Design

Design:

Prospective, randomized, single-blinded clinical trial

Protocol: *Facial Nerve Study*

PI: [name]

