Efficacy of the treatment will be assessed by measuring facial nerve function using the H-B scale I-VI. Two blinded trained otolaryngologist or mid-level provider trained in otolaryngology will determine the efficacy by evaluating each individual study subject via video recording.

10. Assessment of Safety

Risks of intratympanic steroid injections include pain, bleeding, vertigo, otitis media, and tympanic membrane perforation.

The presence or absence of tympanic membrane perforation will be documented at 14 days and 1 month post-treatment. If a perforation is present, the extent of the perforation, type of treatment, and when resolved will be recorded.

All adverse events will be reported to the IRB and the Otolaryngology Department Quality Assurance. Admission of a trial participant to an emergency room or hospital will be recorded.

11. Statistics

A sample calculation was performed for the number of subjects to be enrolled in order to prove superiority of oral steroids + intratympanic steroids over oral steroids alone. The assumption was made that a 20% increase in primary outcome of complete recovery would be significant. A sample size of 25 subjects should detect a difference at a power greater than 80% and an alpha of 0.05. To account for potential testing or data collection errors, we will collect data on 30 subjects treated with oral steroids and intratympanic steroid injections, as well as 30 controls treated with oral steroids only, for a total of 60 subjects. Data will be collected on up to 30 additional subjects that are placed into Group 3 for medical reasons; therefore total number of subjects to be recruited is 90.

12. Direct Access to Source Data/Documents

The investigators will permit study-related monitoring, audits, IRB/IEC review, and regulatory inspection(s) by providing direct access to source data/documents.

13. Quality Control and Quality Assurance

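### Follow-up and video recording stop at H-B I without naming whose score triggers the stop, so a clinic call that may know the arm can cut off the blinded primary outcome

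*Combined protocol and SAP*

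**What the plan says.** Four parts of the protocol bear on who decides recovery and when observation ends.

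- **Section 10, Assessment of Efficacy:** "Two blinded trained otolaryngologist or mid-level provider trained in otolaryngology will determine the efficacy by evaluating each individual study subject via video recording".
- **Section 6, Procedures:** examinations are filmed before treatment and at every follow-up visit, so that two blinded people working independently can judge recovery and grade. The text then adds that "a third unblinded review will be performed by the treating physician". An H-B score is also taken at every clinic visit, with no scorer named.
- **Section 5, Trial Objectives and Purpose:** a different arrangement, in which patients are examined and "scored using House-Brackmann scoring system by a blinded investigator trained in otolaryngology".
- **End of observation:** Section 6, Procedures states: "Follow-up will be completed once full facial nerve recovery to H-B I or for up to one year, whichever comes first". Section 2 and the Follow-Up paragraph of Section 6 likewise end observation at recovery. None of the three names the rater.

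Complete recovery is the primary outcome in Section 11, and time to recovery is the second question in Section 5. Section 11 holds a sample-size statement and no analysis rules. Nothing there says how two reads are combined or how a participant with a discordant last read is counted.

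**The concern.** Blinded reviewers can grade only videos that exist. If a score given in clinic ends the visits, it also ends the recordings, and so fixes how much the blinded reviewers ever see. Patients know their treatment, so blinded assessment is the main protection against expectation effects on a grade that a rater assigns. If the clinic score comes from someone who also knows the arm, that protection is incomplete for complete recovery and for time to recovery, even though the outcome formally belongs to blinded reviewers. Missed visits cannot be recovered at analysis.

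**Working it through.** The plan gives no figure for this point, so there is none to reproduce. The check is a reading of the text followed by simple arithmetic.

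**Step 1. Who can supply the H-B I that ends follow-up?** Section 6, Procedures knows three scorers: two blinded reviewers working from video and the unblinded treating physician. No deadline for the video reads is given, so a blinded read need not be available at the visit. The one scorer in that section who does not depend on video is the treating physician. Section 5, however, has a blinded examiner see the patient. So it is a reasonable inference, not a stated fact, that the call is unblinded.

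**Step 2. What happens after a discordant last read?** Suppose the clinic call is H-B I and the blinded reviewers grade that video above H-B I. Follow-up is closed and no later video is made. On blinded reads the participant can only be a non-recovery or be censored at that visit. Such censoring would be informative, because someone called recovered in clinic is likely to be close to recovery.

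**Step 3. Size.** Inputs: 30 per randomized group (Section 11: "as well as 30 controls treated with oral steroids only, for a total of 60 subjects") and the target ("a 20% increase in primary outcome of complete recovery would be significant"). The protocol does not say whether that 20% is absolute or relative.

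Let k1 and k2 be the numbers in Groups 1 and 2 who (a) are called H-B I in clinic, (b) are graded above H-B I by the blinded reviewers on that video, and (c) would have reached H-B I on blinded reads at a later scheduled visit within the year. Counting them as non-recoveries:

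observed difference (Group 2 − Group 1) = difference with continued visits − (k2 − k1)/30

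- One participant: 1/30 = 3.3 points.
- k2 = 1, k1 = 0: −1/30 = −3.3 points.
- k2 = 3, k1 = 0: −3/30 = −10 points, half of the target if 20% is absolute.
- k2 = 1, k1 = 3: +2/30 = +6.7 points.
- k2 = k1: no shift in the difference, although both recovery rates are too low.

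The counts are assumptions that show the scale. The documents give no information on k1 or k2, so neither sign nor size can be predicted.

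**The case against.** **The outcome is already assigned to blinded raters.** This stands. Sections 6 and 10 (Assessment of Efficacy) both do so, and no text gives the unblinded review an outcome role. A reader might infer that no rule says which score counts, or that the treating physician sets the primary outcome. The documents do not support either reading.

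**The clinic scorer may be blinded.** This stands as a possibility, because Section 5 says so. In that case the stop would not depend on knowledge of the arm, but a discordant last read would still end observation too early, and Sections 5, 6 and 10 would still describe different arrangements.

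**An unblinded tie-break is conjecture.** This also stands. A reader might expect the third score to settle disagreement between the two blinded reads. The protocol is silent on that, so no bias figure for such a tie-break is warranted. What remains is that the disagreement rule is missing.

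**Other visits limit early stopping.** This stands in part. Perforation checks fall at 14 days and 1 month after treatment, and Groups 2 and 3 have an audiogram about 1 month after the third injection. These give reasons to see participants through roughly the first month. They do not cover the monthly phase, and the audiogram does not apply to Group 1.

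**Over-calling in Group 2 would hurt the superiority claim.** On blinded reads this is correct, as Step 3 shows. It supports treating the direction as unknown; it does not remove the problem.

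**Conclusion.** The concern holds in limited form. The plan names blinded reviewers for the outcome, but as written it lets an unattributed clinic call of H-B I end the recordings that those reviewers need. Each participant affected moves an arm's recovery rate by 3.3 points, and time to recovery is affected as well. How many would be affected, in which arm and in which direction is unknown. Knowledge of the arm enters only if the clinic score is the treating physician's, which is likely but not stated. The missing rule for discordant blinded reads and the undefined purpose of the third review are gaps in the text; they do not show that an unblinded score will decide the outcome. The matter should be settled before enrolment.

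**What to change.** 1. State that complete recovery and time to recovery come only from the blinded video reads. Date recovery to the visit that was recorded, not to the day on which the video is read.
2. Pre-specify how the two reads are combined and how disagreement is settled, by a blinded rule that excludes the treating physician. One option is to keep and report both independent reads, then have the two reviewers reach a consensus while still blinded.
3. Continue the already scheduled visits and videos until the blinded reads confirm H-B I or the one-year limit is reached, whatever the clinic score.
4. Give the treating physician's score a stated purpose: a sensitivity analysis only.
5. Reconcile the single examiner in Section 5 with the two video reviewers in Sections 6 and 10 (Assessment of Efficacy), and name the scorer of the H-B grade taken at each visit.

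**Cost:** videos must be read promptly instead of in a batch, and the turnaround is tightest during the weekly visits. Where a read is still pending, the participant attends one more visit that is already in the schedule. No new reviewers and no new type of visit are needed.

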1. General Information / Title Page

Title: Intratympanic Steroid Injection for Treatment of Idiopathic Facial Nerve Paralysis

Working Title: Facial Nerve Study

Project #: 2007139

Version #: 1

Date: 11/21/16

Sponsor: *None*

Faculty Primary Investigator: *[name]*
University of Missouri
Department of Otolaryngology – Head & Neck Surgery
[name]
[name]

Resident Co-Investigator: *[name]*
University of Missouri - Resident Physician
Department of Otolaryngology – Head & Neck Surgery
[name]
[name]

The study will be conducted in accordance with the design and specific provisions of this IRB approved protocol, in accordance with the ethical principles that have their origin in the Declaration of Helsinki, and that are consistent with Good Clinical Practice (GCP) and the applicable regulatory requirement(s). The Principal Investigator will assure that no deviation from, or changes to, the protocol will take place without prior agreement from the sponsor and documented approval from the IRB, except where necessary to eliminate an immediate hazard(s) to the trial participants. The Principal Investigator will promptly report to the IRB and the sponsor any changes in research activity and all unanticipated problems involving risk to human subjects, or others. This trial will be performed in compliance with the protocol, GCP, and all regulatory requirements.

2. Schedule of Events

Recruitment of trial subjects will begin as soon as authorization is granted by the IRB. Clinic and emergency department patterns indicate that we can expect to identify and enroll 20- 25 participants per year. The goal of the study is to include 90 participants over the course of four years and follow until full facial nerve function is recovered or up to 12 months after the completion of treatment, whichever comes first. The expected length of the entire study will vary depending on when all subjects are identified and treatment is completed.

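### Randomised subjects may be removed from the study for non-adherence or plan violation, with no stated provision for their later outcomes or analysis, so loss of the primary outcome could differ by arm

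*Combined protocol and SAP*

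**What the plan says.** Section 7 (Withdrawal Criteria) provides for removal by the Investigator as well as voluntary withdrawal: "They may also be discontinued from the study at the discretion of the Investigator for lack of adherence to study treatment or visit schedules", with adverse events as a further ground. It adds: "The Investigator may also withdraw subjects who violate the study plan, or to protect the subject for reasons of safety or for administrative reasons". Stopping treatment and leaving the study are not separated.

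For what happens next, the section names two records. The first is completion status: "It will be documented whether or not each subject completes the clinical study". The second is safety information that happens to come to light: "If the Investigator becomes aware of any serious, related adverse events after the subject completes or withdraws from the study", those events are written down. It mentions no H-B score or video.

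Section 2 gives a general aim for participants, to "follow until full facial nerve function is recovered or up to 12 months after the completion of treatment, whichever comes first", and Section 6 (Procedures) has a similar rule. Neither says whether it still applies once a subject has been discontinued.

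Under Section 8 both randomised groups take prednisone. Of the controls it says "Patients in Group 1 will not have any further treatment", while Group 2 has three injections.

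Section 11 is a sample-size paragraph. It sets 25 subjects and then says: "To account for potential testing or data collection errors, we will collect data on 30 subjects treated with oral steroids and intratympanic steroid injections", with 30 controls. It states no analysis population and no handling of missing outcomes.

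Of the earlier randomised trial of this treatment, Section 4 says: "Limitations of this study include small sample size and high attrition rate".

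**The concern.** Section 13 rests the integrity of the data on randomisation. That protection lasts only while the subjects compared are the subjects randomised. Section 7 allows some of them to be taken out afterwards, by judgement, on grounds that are not all equally present in the two arms. Whether a subject has kept to the injections can be judged only by someone who knows the arm. Patients are unblinded, the treating physician's review is unblinded (Section 6), and the Investigator is not stated to be blinded when deciding on discontinuation.

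Blinded video reading protects the scoring of recordings that exist. It does nothing for a subject who has left and is no longer recorded. With 30 subjects per randomised arm, a few missing outcomes can move an arm's recovery rate by several points, and outcomes not collected at the time may not be recoverable later.

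**Working it through.** **Step 1: the plan's own allowance.** Section 11 goes from 25 to 30, read here as per arm. The margin is 30 - 25 = 5, or 5/30 = 16.7%, and 25/(1 - 1/6) = 30. The reason given is mistakes in testing or in collecting data; discontinuation is not mentioned. The 25 itself cannot be reproduced, because the control recovery rate, the test and its sidedness are not stated. Nothing below depends on it.

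**Step 2: which non-safety grounds fall on which arm.**

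| Ground in Section 7 | Group 1 | Group 2 |
|---|---|---|
| Visit schedule | yes | yes |
| Adherence: prednisone | yes | yes |
| Adherence: three injections | no | yes |
| Plan violation, administrative | yes | yes |

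The grounds largely overlap. The injections are the one that applies to a single randomised arm.

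**Step 3: formula.** For one arm of 30, let p be the true recovery proportion, k the number excluded from analysis, and r the recovery proportion among those k. The rate in those left is (30p - kr)/(30 - k), so

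shift = (30p - kr)/(30 - k) - p = k(p - r)/(30 - k).

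The documents give none of p, k or r, and do not say that discontinued subjects are excluded from analysis. All four are assumptions.

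**Step 4: illustration.** Take p = 70% in both arms (21 of 30), k = 3 in Group 2 and none excluded from Group 1. The possible results are:

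| Recovered among the 3 excluded | Group 2 rate in the rest | Shift (points) |
|---|---|---|
| 0 | 21/27 = 77.8% | +7.8 |
| 1 | 20/27 = 74.1% | +4.1 |
| 2 | 19/27 = 70.4% | +0.4 |
| 3 | 18/27 = 66.7% | -3.3 |

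**Step 5: range over the assumptions.**
- p = 60%, k = 3: 18/27 = 66.7% (+6.7) to 15/27 = 55.6% (-4.4).
- p = 80%, k = 3: 24/27 = 88.9% (+8.9) to 21/27 = 77.8% (-2.2).
- p = 70%, k = 1: 21/29 = 72.4% (+2.4) to 20/29 = 69.0% (-1.0).
- p = 70%, k = 5: 21/25 = 84.0% (+14.0) to 16/25 = 64.0% (-6.0). This shows only how the limits grow with k. It needs all five exclusions in Group 2 with the same outcome, and five is not a forecast.

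The shift is zero when r = p. It cancels in the comparison if both arms have the same true rate and lose equal numbers with the same outcomes.

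**Step 6: why an analysis rule alone would not be enough.** If all 60 subjects are kept in the denominator and 3 outcomes per arm are missing, the best-case and worst-case treatment differences lie (3 + 3)/30 = 20 points apart. That is as wide as the target effect if it is read as points. It measures uncertainty, not bias, and it shrinks only if the outcomes are collected.

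**The case against.** The plan is silent about outcomes after discontinuation; it does not prohibit collecting them. A reader might infer that discontinued subjects must be lost, but the text does not say so, and the Section 2 follow-up aim is worded for participants generally. This stands, and the point is put as an unstated provision.

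Section 7 is permissive. It could add attrition; it does not show that any will occur. Section 4 gives no cause for the attrition in the earlier trial, so it is not evidence that removal by investigators drives loss.

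Much of the adherence burden is shared: Group 1 also has prednisone and a visit schedule to keep. Section 5 describes the H-B scorer as a blinded investigator. That does not show that the person deciding on discontinuation is blinded, but neither do the documents establish that this person is unblinded. What remains is the injection burden, which falls on one randomised arm only.

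A reader might take Section 11's description of groups by treatment as a plan to analyse subjects as treated. The sentence is a recruitment target, and the randomised groups are defined by assignment elsewhere. The fair statement is that no analysis population is given.

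A reader might also infer a bias towards the injections. Removing only non-recovered Group 2 subjects in a calculation would inflate the chance of a false finding in their favour, but the assumption itself supplies that direction. The documents support none.

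Finally, the remedy has limited reach. It does not recover missed visits or self-withdrawals, and time to recovery would still need its own censoring rule.

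**Conclusion.** The point holds in limited form. Section 7 permits removal of randomised subjects from the study for non-adherence or plan violation. No section provides for their later H-B or video outcomes, states an analysis population, or says how missing outcomes are handled. Because only Group 2 has injections to keep to, loss of the primary outcome could be arm-related. With 3 Group 2 exclusions, none in Group 1 and true recovery of 70% in both arms, the shift lies between -3.3 and +7.8 points; over recovery of 60% to 80% the limits are -4.4 to +8.9. This rests on assumed recovery rates and counts, and on excluded subjects being left out of the analysis. The documents do not support a claim that such loss will happen, that it favours either arm, or that it has any particular size. The plan should be changed here; confidence is medium.

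**What to change.** 1. **Section 7.** State that non-adherence to study treatment and violation of the study plan do not end outcome follow-up. Such subjects keep the scheduled H-B and video visits as far as they are willing and able. Withdrawal of consent, withdrawal for safety or adverse events, and unavoidable administrative causes stay as written, with the reason recorded by arm.
2. **Section 11.** Analyse all randomised Group 1 and Group 2 subjects in the arm assigned. Report missing outcomes by arm and reason, including those from missed visits. Add a sensitivity analysis, for example missing counted as not recovered, plus best case and worst case by arm.

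The sample size does not change. The cost is wording in two sections, some extra visits for subjects who would otherwise have been discontinued, and slightly more analysis. The visits are a real burden for a study with no sponsor, but they are visits already on the schedule.
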